6.4 Week 1, 2, 3, 4, 8, 12, 16, 20, 24 Visits

Participants will be contacted by telephone or in-person at the dialysis unit 1 week after the start of study medications for the occurrence of adverse events (hypotension, headache, gastrointestinal symptoms, and hospitalizations). Those participants tolerating study medication will have the dose increased to ISD/HY 20/35 mg or placebo for the next week. Dialysis treatment records will be reviewed for the occurrence of hypotension and standard of care dialysis labs will be reviewed at each visit. The dose of study drug may be reduced if a participant experiences dose-limiting adverse events, as outlined below.

Participants will be interviewed in-person at the dialysis unit at Week 2, Week 4 and Week 16 for the occurrence of adverse events (intra-dialytic hypotension, headache, gastrointestinal symptoms, and hospitalizations). Dialysis treatment records will be reviewed for the occurrence of hypotension and standard of care dialysis labs will be reviewed. Vital signs and edema will be assessed. In the absence of dose-limiting symptoms, the dose of study medications will be increased following the Week 2 visit. The dose of study drug may be reduced if a participant experiences dose-limiting adverse events, as outlined below. Following each visit, the appropriate dose of study drug will be delivered to study participants. At that time, pill containers will be returned and unused pills counted and destroyed. Participants will be contacted at Week 3 to collect adverse event information.

Following the Week 4 visit, participants will be contacted in-person or by telephone every 4 weeks at their dialysis facilities. Adverse events and tolerability will be reviewed. Dialysis treatment records will be analyzed for the occurrence of hypotension and standard of care dialysis labs will be reviewed. Pill containers will be returned and unused pills counted and destroyed after the Week 16 visit.

The IDS will be notified to proceed with refill of study medication for patients continuing in the study following the Week 1, 2, 4, and 16 visits.

Visit windows will be \pm 3 days for the week 1, 2 and 4 visits and \pm 7 days for week 8-30 visits.

6.5 Week 26 Visit

At the Week 26 (end of treatment) visit, participants will be interviewed in person to review the occurrence of adverse events. Dialysis unit records will be reviewed as above. Pill containers will be returned and unused pills counted. Vital signs and edema will be assessed. Blood will be drawn for long-term storage, for central lab testing of chemistries and blood counts, and for local lab serum pregnancy tests (in pre-menopausal women). End of study TDI echo will be performed as will PET scans. If necessary, this visit can be split into 2 visits to promote scheduling of end of study testing.

6.6 Week 30 Visit

At Week 30, participants will be called or visited at the dialysis unit to determine whether participants are having any adverse effects from the study medications. Dialysis treatment records will be reviewed for the occurrence of hypotension and dialysis unit records will be reviewed.

6.7 Hypotension Procedures

In the event of recurrent intra-dialytic hypotension or serious hypotension not attributable to acute events (e.g. acute myocardial infarction, sepsis), the investigator will review the participant's non-study anti-hypertensive medications, dry weight, and volume status. The participant's clinician will be contacted to consider the following interventions listed in the preferred order of implementation:

- 1) Decrease non-study anti-hypertensive medication(s)
- 2) Increase dry weight if there is no evidence of peripheral or pulmonary edema
- 3) Reduce ultrafiltration rate by increasing dialysis session duration
- 4) Reduce dose of study medication if:
 - a. Peripheral or pulmonary edema is present
AND
 - b. There are no other anti-hypertensive medications prescribed OR other anti-hypertensive medications should not be discontinued (e.g., beta blocker following myocardial infarction)
- 5) Discontinue study medication when reduction below minimal dose is required

Treating clinicians will be free to manage hypotension according to standard clinical practices and are not obligated to follow the study guidelines with respect to non-study medication, fluid removal rate, or dry weight. In contrast, dose reduction or discontinuation of study drug will be directly managed by study staff in accordance with the guideline. All enrolled participants will continue to be followed for the occurrence of adverse events and for end of study cardiac testing regardless of whether study medications are discontinued.

6.8 Headache or Gastrointestinal Symptoms

In the event of persistent headache, nausea, vomiting, diarrhea, or anorexia without alternative cause, the dose of study medication may be reduced.

6.9 Imaging Studies

6.9.1 Echocardiography

The primary echocardiographic endpoint, the early diastolic mitral annular velocity (E'), will be acquired using the apical 4-chamber view at both the septal and lateral positions at the junction of the LV wall with mitral annulus with the measurements averaged. TDI images will be acquired using steerable pulse wave TDI according to standard techniques (typically >100 frames/s with a 2 mm sampling volume). Other standard echocardiographic measurements such as early (E) and late (A) mitral inflow velocity, LV mass index and LV ejection fraction will be obtained during each study. Blinded analyses will be performed off-line using commercial software. In addition, 3 cardiac cycles of 2D TDI data will be obtained at high frequency in the 3 standard apical views for offline measurement of strain rate (SR) and strain using strain quantification software. Mean strain rate and peak systolic strain will be calculated by averaging across the basal segments of each wall.

6.9.2 PET Scan

Individuals will refrain from smoking, exercise, caffeine-containing beverages, or methyl-xanthines for 24 hours before PET studies. Vasoactive medications such as calcium channel blockers, beta-blockers or nitrates will also be withheld for 24 hours. All participants will have PET scans performed while in a semi-fasting state. PET scans will be performed according to the standard rest and stress scanning protocol at Brigham & Women's Hospital. In brief, a transmission scan will be acquired for correction of photon attenuation, and using ^{13}N ammonia ($\sim 0.286 \text{ mCi/kg}$), myocardial blood flow (MBF) will be measured at rest. This will be followed by a regadenoson infusion, adenosine infusion at a dose of $0.14/\text{mg/kg/min}$ (61) or a dipyridamole (0.56 mg/kg administered over 4 min) infusion, to induce hyperemia. At peak hyperemia, a second dose of ^{13}N ammonia will be injected and imaging repeated. Changes in systemic hemodynamics will be measured between baseline and hyperemia. Visual interpretation of the gated myocardial perfusion images will be performed semi-quantitatively using a standard 5-point scoring system and 17 myocardial segments. Summed rest (SRS) and stress scores (SSS) will be calculated as the sum of individual segmental scores, with the difference recorded as a summed difference score (SDS).

Absolute MBF (in ml/g/min) will be computed blindly from the rest and stress images using commercial software and previously validated methods. Serially acquired transaxial images will be re-oriented into short axis slices of the LV and assembled into serial polar maps, and blood pool (arterial input function) and tissue time-activity curves will be generated. Regional and global rest and stress MBF will be calculated by fitting the ^{13}N time-activity curves to a two-compartment tracer kinetic model. CFR will be calculated as the ratio of absolute MBF at stress over rest for the entire left ventricle. In the case of flow defects the primary measure of CFR used will be the CFR over flow defect-free portion of the LV.

7 Statistical Plan

7.1 Sample Size Determination

Sample size considerations were framed using standard study design parameters to ensure 80% power to detect pre-specified effect sizes utilizing intermediate outcomes. However, for this early phase pilot study, the primary focus is directed at providing pilot efficacy, safety and feasibility information, with no attempt to create critical test result regions for standard hypothesis testing. Results will nevertheless provide preliminary estimates needed to guide design of subsequent, more robust studies and will provide information on safety and tolerability events occurring at high event rates which can be incorporated into the design of further studies.

With 8 participants per group, there will be 80% power to detect a change in CFR of 0.75 (unitless measure), assuming a common standard deviation for change in CFR of 0.5¹³⁸⁻¹⁴³. Assuming the common SD of E' is 2.0 cm/s and baseline is 5.8 ± 1.8 cm/s^{39, 144-146}, we will be able to detect a difference of 3.0 cm/s with 80% power. Changes of this magnitude have been observed in other settings^{144, 147, 148}. Baseline variables will be presented using standard descriptive statistics according to distribution. P<0.05 will be considered significant without correction for multiple comparisons given the pilot nature of this proposal.

Although the detectable change in each effect measure is large, detectable differences are, as noted above, clinically relevant. Further, given the pilot nature of this study, additional trials will be required regardless of whether a significant difference in the efficacy measures is detected. Point estimates and standard deviations around these measures will provide the needed estimates of expected change so that more robust studies can be designed.

It is similarly noted that under the proposed sample size, estimates of safety and tolerability event rates will provide relatively crude estimates of the true event rates. Confidence intervals around estimated event rates based on various observed event rates within the treatment (or control arm) will be large and are provided below for a range of detected event rates (Table 1). As shown in Table 2, power to detect event rates $\geq 20\%$ will be good while power to detect lower event rates within each study arm will be limited for events with a true rate <15%.

Table 1. Confidence interval for estimated event rates within each study arm

Observed Events	Observed Event Rate	Low Bound 95% CI	Upper Bound 95% CI
0	0.00	0	0.37
1	0.125	0.00	0.53
2	0.25	0.32	0.65
5	0.625	0.24	0.91
8	1.00	0.63	--

Table 2. Detectable event rates

True Event Rate	Power (Detection Probability)
0.05	0.34
0.10	0.57
0.15	0.73
0.20	0.83
0.25	0.90
0.30	0.94

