7.4 Statistical Methods

In addition to the analyses described subsequently, descriptive statistics will be used during the course of the project as part of data management procedures for monitoring data quality. A brief overview of some of the statistical methods that may be used at the time of analysis, both for descriptive purposes and in more comprehensive analysis of the primary research questions, is summarized in the following

sections. It is recognized that these methods may be revised and additional ones considered as the details of the specific analyses are developed.

Given the pilot nature of this study, the primary objectives of this study are to derive pilot estimates of efficacy and safety. As noted above, given the small sample size, the power to detect small to medium effect sizes or adverse event rates will be limited. However, the point estimates and confidence intervals around effect sizes and adverse event rates are expected to provide information needed for the planning of future studies.

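### Table 1 gives a 95% lower bound of 0.32 for 2 events in 8, above the row's own estimate of 0.25; the exact bound is 0.03

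*Combined protocol and SAP*

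**What the plan says.** Section 7.1 sizes the trial on the two efficacy measures ("With 8 participants per group, there will be 80% power to detect a change in CFR of 0.75", with a parallel statement for E'). It then turns to safety and tolerability and warns the reader: "Confidence intervals around estimated event rates based on various observed event rates within the treatment (or control arm) will be large". The illustration of that warning is headed "Table 1. Confidence interval for estimated event rates within each study arm" and lists 0, 1, 2, 5 and 8 observed events, with a column labelled "Low Bound 95% CI" and a matching upper-bound column. The interval method is not named.

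The row at issue is "2 0.25 0.32 0.65" (events, rate, lower, upper). Its neighbours are "1 0.125 0.00 0.53" above and "5 0.625 0.24 0.91" below. Section 7.4 returns to these intervals when it says that "confidence intervals around effect sizes and adverse event rates are expected to provide information" for planning later studies.

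**The concern.** Two features of the row are impossible, and both can be seen without calculation.

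- **The interval misses its own estimate.** The observed rate is 0.25 and the interval starts at 0.32. None of the standard 95% intervals for a proportion does this.
- **The lower-bound column is out of order.** With n fixed, the lower bound must rise with the number of events. Down the table it runs 0, 0.00, 0.32, 0.24, 0.63. Only the 0.32 breaks the sequence.

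The only purpose of Table 1 is to show how little 8 participants per arm can say about an event rate, and safety and tolerability are among the primary objectives (Section 2.1). Taken at face value, the row says that 2 events in 8 would rule out a true rate below 32%. Two events in an arm is a plausible result, so a reader may well look this row up.

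**Working it through.** **Inputs.** n = 8 per arm (Section 7.1). Confidence level 95% with both bounds given, so 0.025 in each tail (Table 1 column labels). Event counts x = 0, 1, 2, 5, 8 (Table 1).

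**Step 1: confirm the denominator.** Table 2 should be the probability of seeing at least one event, 1 − (1 − p)^8. For p = 0.05, 0.10, 0.15, 0.20, 0.25 and 0.30 this gives 0.337, 0.570, 0.728, 0.832, 0.900 and 0.942. The table has 0.34, 0.57, 0.73, 0.83, 0.90 and 0.94. All six agree, so n = 8 is the base.

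**Step 2: identify the interval method.** The exact (Clopper-Pearson) limits are:

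- lower = 2.5th percentile of Beta(x, n − x + 1), with 0 when x = 0
- upper = 97.5th percentile of Beta(x + 1, n − x), with 1 when x = n

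| Events | Exact lower | Table 1 lower | Exact upper | Table 1 upper |
|---|---|---|---|---|
| 0 | 0 | 0 | 0.3694 | 0.37 |
| 1 | 0.0032 | 0.00 | 0.5265 | 0.53 |
| 2 | **0.0319** | **0.32** | 0.6509 | 0.65 |
| 5 | 0.2449 | 0.24 | 0.9148 | 0.91 |
| 8 | 0.6306 | 0.63 | 1 | not given |

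Table 1 contains nine numeric bounds. Eight match the exact method after rounding, including the upper bound in the disputed row. The ninth is the 0.32.

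**Step 3: check the exact lower bound from its definition.** The lower limit is the rate p at which P(X ≥ 2) = 0.025, where P(X ≥ 2) = 1 − (1 − p)^8 − 8p(1 − p)^7.

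- At p = 0.0319: 1 − 0.7715 − 0.2034 = 0.025, as required.
- At p = 0.32: 1 − 0.0457 − 0.1721 = 0.782. With a true rate of 0.32, two or more events would be the usual result, so 0.32 cannot be a lower limit for 2/8.

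**Step 4: try other methods for 2/8.**

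| Method | Lower | Upper |
|---|---|---|
| Normal (truncated at 0) | 0 | 0.550 |
| Jeffreys | 0.056 | 0.592 |
| Agresti-Coull | 0.063 | 0.599 |
| Wilson | 0.071 | 0.591 |
| Exact | 0.032 | 0.651 |

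None comes near 0.32, and only the exact method gives the row's upper bound of 0.65.

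**Step 5: rule out a value copied from another row.** The exact lower bounds for 3, 4, 5, 6 and 7 events in 8 are 0.085, 0.157, 0.245, 0.349 and 0.474. None rounds to 0.32.

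**Step 6: size of the error.** Lower bound 0.32 against 0.032, a factor of 10. Width 0.65 − 0.32 = 0.33 against 0.6509 − 0.0319 = 0.619, so the row shows about 53% of the exact width.

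**The case against.** The best counter-argument is about provenance. The case rests on one digit string in a table converted from PDF, and conversion can lose a zero. That possibility stands, but it is the less likely one: the row has all four cells in order, and the other three are correct. No other bound in the table has more than two decimals, so a source entry of 0.032 would have been out of format.

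A second objection is that the method is not named, so 0.03 is an inference. Other methods would give 0.06 or 0.07. The inference is strong, because eight bounds match the exact method and none of the alternatives reproduces 0.65. That 0.32 is wrong does not depend on the method at all.

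A third objection is that nothing turns on the cell, and this largely stands. The sample size rests on CFR and E', Table 2 does not use the cell, no interim analysis is planned (Section 7.4.3) and no decision rule refers to the table. The surrounding text already says the estimates will be crude. An attentive reader will see that 0.32 exceeds 0.25 and take it for a misprint. That limits the weight of the point but does not make the figure right.

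**Conclusion.** The lower bound for 2 events in Table 1 is wrong as it stands. It contradicts its own row and column under any standard method. Given n = 8 and the exact method that reproduces every other bound in the table, it should be 0.03. A dropped zero (0.032 becoming 0.32) is the likely cause, though the documents cannot confirm it. This is a minor arithmetic error: it misstates one illustrative precision figure for a primary safety objective and has no effect on the design, the sample size or the planned analyses.

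**What to change.** Check the cell against the source page. If it shows 0.32, change the low bound in the row for 2 observed events to 0.03, so that the interval is 0.03 to 0.65. No other cell in Table 1 or Table 2 needs changing. The cost is one table cell, with no extra participants.

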7.2 Randomization and Stratification

To ensure balance in treatment assignments within potential confounders, a stratified randomization procedure, based on LVEF <=45% will be implemented. Within each of these strata, participants will be randomly allocated to the ISD/HY or placebo in a ratio of 1:1.

In order to maintain blinding, ISD, HY, and placebo preparations for each arm will have an identical appearance, and the same number of tablets will be prescribed for each participant. The treatment assignment code, corresponding to each treatment identifier number, will be known only to the IDS, until the completion of treatment and data collection on all participants. This information may also be known to the dispensing pharmacists. The study participants, and all other members of the investigative team, will remain blinded to the treatment assignment, including the investigator, the biostatisticians, the study nurses, and referring physicians.

7.3 Intent-to-treat Analysis and Missing Data

An intent-to-treat analysis, in which all available data on all randomized participants are included, will be used for the primary comparison of treatments. All attempts will be made to keep missing data to a minimum, and participants who withdraw from treatment will be encouraged to continue on study in order to provide complete follow-up information. Thus, irrespective of withdrawal from treatment, all participants should continue to be followed with all scheduled outcome evaluations until the end of the study. However, it is expected that up to 10% of the randomized participants may withdraw prior to the final assessment of response at 26 weeks. These participants will be included in the denominator for evaluation of the response rates defined for the primary endpoint.

The characteristics at the time of randomization for those participants without complete follow-up will be examined; however, there will be limited statistical power to detect any but major differences between these participants and those with complete follow-up. In addition, in order to assess the potential biases introduced by differential withdrawal among treatment arms, a comparison of withdrawal rates and/or time to withdrawal will be included as an ancillary analysis to the primary endpoint comparison.

Secondary analyses will examine the all-treated, as-treated, and per-protocol populations as defined below. Given the pilot nature of this study and small sample size, no corrections will be made for

multiplicity in these additional analyses. The possibility of false-positive results is acknowledged and results of these analyses will be considered strictly exploratory.

Nevertheless, these secondary analyses may provide important, hypothesis-forming insights into mechanism of action and optimal design for further studies in the event that significant deviations from the protocol or dropout from the study are felt to have had an important impact on the results.

The analysis populations are defined as follows:

- All-randomized / intention-to-treat (ITT) population: Any participant randomized into the study, regardless of whether study drug was received.
- As-treated population: The as-treated population is the same as the ITT population (i.e., any participant randomized into the study regardless of whether study drug was received). However, for the as-treated analysis, patients in the active drug group who did not receive at least one dose of study drug will be classified into the placebo arm.
- All-treated population: Any participant randomized into the study who received at least one dose of study drug.
- Per-protocol population: Any participant who was appropriately randomized, and received the protocol-dictated study drug exposure ($\geq 75\%$ of prescribed doses) and endpoint assessments through 24 ± 2 weeks.

Because dose-related efficacy and safety are important questions of interest in this study, the ITT analysis will be supplemented with an analysis of the as-treated population. Although ITT approaches provide the least-biased analysis of treatment efficacy and safety, as-treated analyses provide important complementary information on biological effectiveness of therapy (e.g. theoretical efficacy if drug were tolerated by all participants) and on the effects of actual doses used that is not captured by (ITT) analyses in which the unit of analysis is a randomized therapy that may not have been used by individual participants¹⁴⁹. For this reason, as-treated approaches provide important complementary information to ITT analyses and are typically mandated as an important secondary analyses of clinical trials by the FDA¹⁴⁹. Given a treatment protocol that allows for dose reduction of study medications, the as-treated analysis will provide critical information in this trial for assessing dose-related efficacy and the incidence of adverse events such as hypotension. As-treated analyses will assign treatment dose according to the dose used at the time of an adverse event (safety analyses) or according to the mean dose received during the trial (efficacy analysis).

In general, missing data will not be imputed. Every effort will be made to use statistical methods that are robust to missingness, and the number of participants included with each analysis will be given with the results.

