3.1 General Design

[figure not shown]
This is a randomized, placebo-controlled 2-arm trial that will compare placebo with ISD/HY combination therapy. Participants will be randomized in a 1:1 fashion to ISD/HY or placebo. As shown in Figure 4, the study will be conducted in 2 phases: a 4-week dose escalation phase and a 22-week treatment phase.

All randomized participants will initiate treatment with therapy three times daily. The active therapy group will receive a one-week supply of ISD/HY 10/10 followed by a one-week supply of ISD/HY 20/35 3x/day. The placebo control group will receive an identical supply of placebo and will follow the same

schedule as the active therapy group. At the 1 week and the 2 week visits, tolerability and hypotension will be assessed. If the starting dose and first dose titration is tolerated, participants will be increased to ISD/HY 40/75 mg 3x/day (active therapy) or placebo and they will receive an additional 2 weeks drug supply. Tolerability will be re-evaluated after an additional 2 weeks and at 4 week intervals thereafter. At 4 weeks, participants tolerating the full dose will receive a 12-week supply of study medication at the appropriate dose. At 16 weeks, an additional 10-week supply will be provided. Participants not tolerating the full dose at this point may reduce to the starting doses of active therapy at this visit. In the event of poor tolerance or drug related adverse events (e.g. hypotension, intra-dialytic cramping), the dose of study medication may be held or reduced to a minimum dose of ISD/HY 10/10 mg 3x/day (active therapy) or matched placebo 3x/day. Except where un-blinding is necessary for safety purposes, participants not tolerating the lowest dose of active therapy will be reduced to double placebo therapy in order to maintain unbiased assessments of study endpoints.

In order to maintain the blind, all study participants, regardless of randomized assignment, will receive new dosing kits within 1 day (with a window of up to 3 days) of the 1, 2, 4, and 16 week visits, and will be evaluated bi-weekly during the dose escalation phase.

Figure 4. Study Design

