7.4.1 Descriptive Analysis

Standard descriptive statistics will be used to summarize baseline characteristics and study outcome measures at each follow-up visit, both overall and within each treatment group. Examination of baseline characteristics will include estimates of the distribution of age, race, and other demographic characteristics, lab measures and study center. Summary statistics such as means, medians, and ranges will be produced for all measured variables. Frequencies will be computed for all categorical and ordinal variables. Graphical methods including stem-and-leaf diagrams and boxplots will be used to examine distributions, identify potential influential points, and guide in the choice of transformations, if warranted. The balance of baseline measures across the treatment groups will be compared using appropriate k-sample tests, including X-Squared tests and Fisher's exact tests.

Analysis of Primary Efficacy and Safety Outcomes Mean \pm standard deviation or median (interquartile values) of baseline and end of study measurement in the primary endpoint E' will be presented. Change in E' velocity or CFR at 26 weeks will be assessed and reported quantitatively, and descriptive statistics for absolute and % change will be provided. Mixed effects linear regression models with baseline covariate adjustments will be used for assessment of treatment effects. Model assumptions regarding homoscedasticity and normality will be examined using standard techniques.

For the safety endpoints, tables with percent incidence and incidence rate (for events that can occur more than once during follow-up) will be prepared. Differences in incidence and incidence-rate will be assessed using logistic regression or Poisson regression with factors for assigned treatment and the stratification variable. In particular, for safety endpoints, we will investigate the potential shift in blood pressure in control and treatment groups with monthly measure of blood pressure. We will use mixed effects linear regression models to assess the direction and time averaged magnitude of change in potassium, with and without controlling for baseline covariates. The proportion of serious hypotension in treatment and control groups will be compared with Chi-square test or Fisher's exact test.

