The primary analysis will examine the intention to treat population. Exploratory analyses will be repeated in the as-treated, all-treated and per-protocol populations (see **Section 7.3**) using analogous techniques. $P<0.05$ will be considered significant in all analyses.

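### The as-treated safety analysis assigns a dose only when an adverse event occurs and states no exposure time by dose, so event counts by dose would largely follow time spent at each dose

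*Combined protocol and SAP*

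**What the plan says.** Section 7.3 supplements the intention-to-treat analysis with an as-treated one. The only regrouping it defines is that "patients in the active drug group who did not receive at least one dose of study drug will be classified into the placebo arm". It creates no groups by dose level.

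Dose enters through a separate rule. For safety: "As-treated analyses will assign treatment dose according to the dose used at the time of an adverse event (safety analyses". For efficacy, the same sentence continues: "or according to the mean dose received during the trial (efficacy analysis". The section attaches weight to the result: "the as-treated analysis will provide critical information in this trial for assessing dose-related efficacy and the incidence of adverse events such as hypotension".

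Section 7.4.1 says that, for safety endpoints, "tables with percent incidence and incidence rate (for events that can occur more than once during follow-up) will be prepared". Differences are to be assessed by "logistic regression or Poisson regression with factors for assigned treatment and the stratification variable". It then adds: "Exploratory analyses will be repeated in the as-treated, all-treated and per-protocol populations", by analogous methods. Dose is not among the model factors.

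Section 7.3 also makes intention-to-treat the primary comparison and calls the other analyses exploratory.

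**The concern.** The safety rule defines exposure through the outcome. A participant with an event has a dose for that event. A participant without one has no dose, and neither does an event-free week. The efficacy rule does not have this problem, because mean dose received does not depend on having an event.

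The methods in Section 7.4.1 do not fill the gap as written. A logistic model by dose needs a dose for people without events, and a Poisson model by dose needs time at each dose. Neither is defined.

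The titration schedule is very uneven. Anyone who follows it spends nearly all the treatment period at the top step, so a table of events by dose at onset could look like a dose response when there is none. The protocol says that its doses were chosen without dialysis-specific data (Section 1.4) and that its estimates will guide later trials (Sections 7.1 and 7.4). A misleading dose pattern for hypotension could carry over into those designs.

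**Working it through.** **Inputs.** The plan gives no figure for events or exposure by dose, so the check starts from its schedule.
- Treatment period: "a 4-week dose escalation phase and a 22-week treatment phase" (Section 3.1), so 4 + 22 = 26 weeks. The drug supplies in Section 5.3 agree: 1 + 1 + 2 + 12 + 10 = 26 weeks.
- First step 1 week, second step 1 week, top step from Week 2 (Study Summary; Section 5.2). On schedule, the top step lasts 26 − 2 = 24 weeks.
- Section 5.2, in its text on interrupted escalation, instead gives 2 weeks for the second step. The top step would then last 26 − 3 = 23 weeks.
- 16 participants randomised 1:1, so 8 on active drug (Section 5.2) and 8 × 26 = 208 active patient-weeks.

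**Formula.** Expected share of events at the top step = (top-step weeks × top-step rate) / sum over steps of (weeks × rate).

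**Constant rate, all on schedule.** 24/26 = 92.3% at the top step and 1/26 = 3.8% at each lower step, a 24:1 ratio of counts with no dose effect. With a 2-week second step: 23/26 = 88.5%.

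**Top-step rate lower than the rate at the other steps, all on schedule.**
- Half: 12/(12 + 2) = 85.7%.
- A quarter: 6/(6 + 2) = 75%.
- One twelfth: 2/(2 + 2) = 50%.

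**Constant rate, m of 8 participants reduced for good at Week 4.** Each of them has 4 − 2 = 2 top-step weeks, so the share is [(8 − m) × 24 + 2m] / 208. The value of m is assumed, because the plan gives no reduction rate.

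| m | Top-step patient-weeks | Share |
|---|---|---|
| 0 | 192 | 92.3% |
| 1 | 170 | 81.7% |
| 2 | 148 | 71.2% |
| 3 | 126 | 60.6% |
| 4 | 104 | 50.0% |
| 5 | 82 | 39.4% |

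If 4 of 8 never reach the top step, the share is 4 × 24/208 = 46.2%. In every row the share equals the fraction of exposure time at the top step.

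**Percent incidence by dose at event.** This needs an invented dose for event-free participants. Suppose they are given their final dose and everyone stays on schedule. Then everyone classified at a lower step has had an event, so incidence there is 100% by construction. The same data would point the opposite way from the counts.

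**With patient-weeks as the denominator.** On schedule, the 8 active participants contribute 8, 8 and 192 patient-weeks. Take 20 events with no dose effect (an illustration). Expected counts are 20 × 1/26 = 0.77, 0.77 and 20 × 24/26 = 18.46. The rate is 20/208 = 0.096 per patient-week at every step, so the artefact disappears.

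**Precision.** With zero events, the exact upper 95% limit is −ln(0.025)/T = 3.689/T. That is 3.689/8 = 0.46 per patient-week at one lower step, against 3.689/192 = 0.019 at the top step.

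**Recurrent hypotension.** Section 3.2.1 defines it over a rolling 30-day period. For a participant on schedule, a window covering days 1 to 30 includes both lower steps (14 days) and 16 days at the top step. The dose at the time of such an event is not defined.

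**The case against.** The strongest reply is that the plan is silent on dose-specific person-time but does not reject it. Assigning an event to the dose in use at onset is an ordinary numerator rule for time-varying exposure. Section 7.4.1 plans incidence rates and Poisson regression and extends them to the as-treated population by analogous methods, so a sensible analyst could supply time at each dose. No section proposes comparing raw counts. Section 7.4 says that methods may be developed further.

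Much of this stands, and it limits the point. A reader might infer that the analysis has no denominator at all. The documents do not support that: rates by arm are planned, and what is missing is a stated denominator by dose. A reader might also infer that most events will appear at the top step whatever the drug does. That does not follow either. Poor tolerance leads to dose reduction, and the share falls to half or less once 4 of 8 are reduced at Week 4. Reduction after an adverse event also moves the more susceptible participants to lower doses, a bias in the opposite direction.

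The reply does not remove the gap. The only dose rule that the plan writes for safety depends on having an event, and the models it names use assigned treatment and stratum. The exploratory label covers false-positive findings; it does not supply an exposure definition.

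**Conclusion.** The point holds in a limited form. As written, the as-treated safety analysis cannot give a valid rate by dose, because dose is defined by the event and no time at each dose is stated.

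The 92% figure applies to raw counts with full adherence and a constant event rate. It becomes 88.5% under the longer second step and about 50% if 4 of 8 are permanently reduced at Week 4. No single figure can be predicted, because the reduction rate is unknown. What is consistent is that, at a constant rate, the counts follow exposure time.

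The defect is confined to an exploratory analysis. The primary intention-to-treat safety comparison and the event rates by arm are untouched. It still merits correction, because the plan relies on this analysis for dose-related information on events such as hypotension.

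**What to change.** Amend Sections 7.3 and 7.4.1 as follows:
- Treat dose as time-varying. Use patient-weeks at each dose, with time off drug as its own category, as the offset in the Poisson model, with a participant-level or robust error term.
- Take dose dates from the drug request and kit records in Sections 5.2 and 5.3. Count the interval in which a participant has stopped while awaiting a lower-dose package as off drug.
- Show placebo patient-time and events at the same nominal step. Placebo follows the identical schedule (Section 5.2), and for participants on schedule dose is otherwise confounded with time since randomisation.
- State how an event defined over the rolling 30-day window is assigned when the window spans several doses.
- Label the result non-randomised and exploratory. Person-time corrects for unequal exposure; it does not remove the confounding from dose reduction after adverse events.
- Reconcile the 1-week and 2-week statements on the second step, because they change the denominators.

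The cost is SAP wording and some programming. The price in precision is plain: about 8 active patient-weeks at each lower step against 192 at the top if all stay on schedule. Robust errors are unreliable with 8 per arm, so the main output should be rates with exact intervals. Because those intervals treat repeat events in one person as independent, also give the number of participants contributing events.
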